Title: Development and Evaluation of a Theory and Evidence-based Intervention to Reduce Hazardous Alcohol Consumption Among Treatment Seeking Smokers

NCT number: not yet assigned

Document date: October 20, 2025

Project background

We will measure the adoption of the alcohol resource in the patient portal by examining analytics data, which will be passively collected by the STOP patient portal. Given the evidence supporting the digital alcohol interventions that will be adapted for this population, and the larger sample that would be needed for an efficacy study, we will not directly evaluate the efficacy of the intervention in this study.

Specifically, we will test whether more eligible STOP patients accept the alcohol resource with the patient portal than did when it was offered by health care providers in the COMBAT, the cluster randomized control trial we conducted previously. In that study, 52.7% of participants scoring 8+ on the AUDIT-10 received an offer and 15.4% (95%CI = 13.9%, 17.1%) of the total sample (29% of those receiving an offer) accepted it. Reanalysis of COMBAT data showed that patient characteristics were minimally predictive of offer receipt and acceptance, while provider-level variance was substantial in both cases (ICCs \geq 0.50). This suggests that provider willingness to offer the intervention was the primary reason for the moderate offer proportion. In this study, we anticipate a similar acceptance rate, but will make the offer to all participants, yielding an anticipated acceptance rate of 29%.

Outcomes

Our primary outcome is **acceptance of the offered intervention**, defined as a response of 'yes' to the question, "Are you interested in receiving some information about alcohol and smoking and about ways of reducing alcohol use?"

Our secondary outcome is **continued participation in smoking cessation treatment**.

Analysis plan

Primary outcome: We will analyze the primary outcome using a chi-square test comparing the proportion in the present study to that in the original COMBAT project. We will use a significance level of 0.05 and will derive confidence intervals around both proportions and around the difference between them.

Sensitivity analysis: To examine the potential sensitivity of this result to case-mix differences, we will use logistic regression to compare adoption in this sample to that among COMBAT participants with AUDIT scores of 8 or higher. Due to the small size of the sample in the current study, we will use propensity score weighting to adjust for age, gender, heaviness of smoking, AUDIT scores, education, income, and comorbid conditions. To account for sporadic missingness in these variables, we will use multiple imputation, with the number of imputed datasets dependent on the observed level of missingness.

Secondary outcome: For our secondary outcome, we will compare the proportion of participants who do not attend a clinical visit after self-enrolling to that among people self-enrolling before the study began who would have met study criteria. We will not examine longer-term retention due to the study timeline and the expectation that effects would be visible at the first contact.

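### Does the primary test compare the portal with the wrong COMBAT acceptance rate, or on unlike denominators?

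*SAP*

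**What the plan says.** Project background states the hypothesis as a question of whether more of the eligible patients "accept the alcohol resource with the patient portal than did when it was offered by health care providers in the COMBAT". For COMBAT it puts the offer rate in the AUDIT 8+ group at 52.7%. On acceptance it reports: "15.4% (95%CI = 13.9%, 17.1%) of the total sample (29% of those receiving an offer) accepted it". The moderate offer proportion is attributed mainly to providers' willingness to make the offer, with provider-level ICCs of at least 0.50. For the present study the SAP says "we anticipate a similar acceptance rate, but will make the offer to all participants, yielding an anticipated acceptance rate of 29" per cent.

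Outcomes names the primary outcome as "acceptance of the offered intervention", meaning a 'yes' to a question about interest in receiving information. Under Analysis plan, the primary outcome is tested by chi-square against the COMBAT proportion at the 0.05 level, with confidence intervals for both proportions and for their difference. That sentence does not give the COMBAT proportion as a number. The sensitivity analysis compares adoption with that of COMBAT participants whose AUDIT scores were 8 or higher.

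**The concern.** Read alone, the outcome label and the second half of the hypothesis sound like acceptance per offer. In COMBAT that quantity is 29%, the very rate anticipated for the portal, so a test of one against the other would have nothing to detect.

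If 15.4% is meant, a second worry follows. That rate counts the 47.3% of COMBAT patients who were never offered the resource as non-acceptors. The portal outcome is a 'yes' to a question, and the SAP does not say how eligible patients who skip or never reach the question are counted. Leaving them out would raise the portal rate against a comparator that keeps every non-offered patient in.

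Third, a significant result against 15.4% could arise even if patients accept the portal's offer less readily than a provider's. The SAP plans no per-offer comparison that would show this.

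**Working it through.** **Inputs from the SAP (Project background).** COMBAT offer rate 52.7%; acceptance 15.4% of the total sample (95% CI 13.9% to 17.1%); acceptance 29% of those offered; anticipated portal rate 29%; significance level 0.05.

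**Inputs assumed.** The SAP gives neither the COMBAT sample size nor the portal sample size. From the half-width of the COMBAT interval, (17.1 − 13.9)/2 = 1.6 points, the Wald formula gives N = 0.154 × 0.846 × (1.96/0.016)² ≈ 1,955. Wilson intervals that round to the stated limits give 1,908 to 1,995. I take N = 1,950, of whom 0.527 × 1,950 ≈ 1,028 were offered. For the portal I take n from 50 to 300.

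**1. The SAP's own figures agree.** 15.4/52.7 = 29.2%, which rounds to the stated 29%. So the total sample behind 15.4% is the AUDIT 8+ group, and the two rates differ only in denominator.

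**2. What depends on the comparator.**

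| Comparator | Expected difference | Power, n = 50 | n = 100 | n = 200 |
|---|---|---|---|---|
| 15.4% of all AUDIT 8+ (N ≈ 1,950) | 29 − 15.4 = 13.6 points | 70% | 91% | 99% |
| 29% of those offered (N ≈ 1,028) | about 0 | 5% | 5% | 5% |

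These figures treat COMBAT patients as independent. With provider ICCs of at least 0.50 the first row is optimistic, but the contrast between the rows remains.

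**3. Which comparator the text supports.**

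- The subject of the hypothesis is eligible patients. Its closing clause about providers reads naturally as the mode of delivery, portal versus provider.
- Of the two COMBAT acceptance rates, only 15.4% carries a confidence interval, and the primary analysis calls for intervals around both proportions.
- The rationale holds acceptance per offer constant and extends the offer to everyone. That predicts a gain over 15.4% and none over 29%.
- The sensitivity analysis examines the same result for case-mix. Its comparator is COMBAT participants with AUDIT 8+, with no restriction to those offered.

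All four point to 15.4%. None points to 29%.

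**4. Denominators.** The SAP says "will make the offer to all participants, yielding an anticipated acceptance rate of 29" per cent. When everyone is offered, the per-offer and per-eligible groups in the present study are the same people, so 29% versus 15.4% compares all eligible with all eligible. A mismatch would need a rule that drops patients without an answer, and the SAP contains none. If such a rule were applied, 29% among those answering would be 0.29 × 0.90 = 26.1% of all eligible with 10% non-response, or 0.29 × 0.80 = 23.2% with 20%. Both non-response rates are assumptions.

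**5. Winning with a lower per-offer rate.** Against 300/1,950 (15.4%), the smallest observed portal rate with Pearson p < 0.05 is 26% (n = 50), 23% (n = 100), 21% (n = 200) or 20% (n = 300). All lie below 29%. At n = 100, the Wilson 95% interval for 23/100 is about 16% to 32%, which includes 29%, so that result would not show the portal offer to be less acceptable. At n = 200, the interval for 42/200 is about 16% to 27% and excludes 29%. Whether the case arises clearly depends on a sample size the SAP does not give.

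**The case for a change.** The strongest case for a change is that a SAP exists to fix such choices before the data are seen. Here one unnamed number separates a test with a 13.6-point expected difference from one with none. The outcome label, read literally, matches the COMBAT rate described as "29% of those receiving an offer) accepted it". Sending the offer to everyone is an intention and not a rule for non-response, and the multiple imputation in the sensitivity analysis covers only the adjustment variables. Two sentences and one extra two-by-two table would cost almost nothing.

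Part of this stands. The chi-square sentence does not name 15.4%, and the treatment of patients without an answer is not written down. The consequence does not follow, because an analyst who chose 29% would contradict both the rationale and the sensitivity analysis. On non-response, defining the outcome by a 'yes' removes nobody from the denominator, and it fits equally well with counting everyone else as not accepting. Whether the portal question is mandatory is commonly left to the protocol, which is not at hand.

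The request for a per-offer comparison is a preference. A gain through universal offering is what the study sets out to show, and the SAP says so. COMBAT's 29% also comes from the 52.7% whom providers offered the resource, with substantial variation between providers, so a formal contrast with it would be hard to interpret. The planned interval around the portal proportion already lets a reader set it beside 29%.

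**Conclusion.** The concern does not call for a change. The arithmetic behind it is right: 15.4/52.7 = 29.2%, and the choice of comparator would decide whether the test has anything to detect. But the SAP leaves only one coherent reading, namely acceptance among all eligible AUDIT 8+ patients in both sources, with COMBAT at 15.4% and an expected difference of 13.6 points. The zero-difference test is not the one planned. Unlike denominators would arise only under a rule the SAP does not contain, and the size of that effect rests on assumed non-response.

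The residue is missing detail that a competent analyst fills as the plan implies: 15.4% as the comparator, and any eligible portal patient without a 'yes' counted as not accepting. Writing this down would record what is already implied and would not alter the analysis. The conclusion about the comparator rests on the SAP's wording alone. The power and threshold figures also rest on a COMBAT N of about 1,950, portal samples of 50 to 300, and independence between patients.

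### The primary chi-square treats COMBAT patients as independent, although the SAP describes COMBAT as cluster randomised with provider-level ICCs of at least 0.50

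*SAP*

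**What the plan says.** Under Project background, the SAP introduces COMBAT as "the cluster randomized control trial we conducted previously" and gives its acceptance as "15.4% (95%CI = 13.9%, 17.1%) of the total sample". It reports that for offer receipt and acceptance "provider-level variance was substantial in both cases", with ICCs of at least 0.50, and concludes: "This suggests that provider willingness to offer the intervention was the primary reason for the moderate offer proportion".

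Under Analysis plan, Primary outcome, acceptance is to be analysed "using a chi-square test comparing the proportion in the present study to that in the original COMBAT project" at a significance level of 0.05. The authors "will derive confidence intervals around both proportions and around the difference between them", without naming an interval method.

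Under Sensitivity analysis, "we will use logistic regression to compare adoption in this sample to that among COMBAT participants with AUDIT scores of 8 or higher", with propensity weighting and multiple imputation. The weighting is explained with the words "Due to the small size of the sample in the current study"; no number is given. Neither analysis mentions clustering.

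**The concern.** The ordinary chi-square assumes that every patient's response is independent. The SAP's own reanalysis says the opposite about COMBAT: whether a patient was offered the resource and accepted it depended heavily on the provider. COMBAT's 15.4% therefore carries provider-sampling variance that the test leaves out. COMBAT is not treated as a fixed benchmark, since the SAP plans an interval around its proportion and around the difference.

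With a positive ICC and more than one patient per provider, the direction is certain: the comparator's variance is understated and the nominal 5% test rejects too often. This test is the study's main answer. The sensitivity regression addresses case mix only and does not repair it.

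For the intervals the point is conditional. The COMBAT interval and the difference interval will be too narrow only if they use the same binomial variance. The portal proportion's own interval is unaffected.

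**Working it through.** **Inputs from the SAP.** COMBAT offer rate 52.7%; acceptance 15.4% (13.9% to 17.1%); anticipated portal acceptance 29%; provider ICCs at least 0.50; alpha 0.05 (taken as two-sided).

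**The SAP's own figures.** 0.154 / 0.527 = 29.2% and 0.527 × 0.29 = 15.3%, so the 29% and 15.4% agree within rounding.

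**COMBAT's n.** It is not stated. The interval's half-width is 0.016, so n ≈ 1.96² × 0.154 × 0.846 / 0.016² ≈ 1,955. A Wilson interval reproduces the printed limits at n 1,908-1,995 if the proportion is exactly 15.4%, or about 1,847-2,086 once its rounding is allowed for. I use 1,950, with two readings:
- Reading A: 1,950 is the raw n, and the quoted interval ignores clustering.
- Reading B: 1,950 is the effective n, and the quoted interval is already cluster-adjusted.

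**Assumptions.** Portal n of 50, 100 or 200. Patients per provider m from 2 to 20. ICC from 0.30 (roughly what a latent logistic 0.50 becomes on the observed scale at 15.4%) to 0.50. With design effect DE = 1 + (m − 1) × ICC, the range is 1 + 1 × 0.30 = 1.3 to 1 + 19 × 0.50 = 10.5. The SAP's 0.50 is a minimum, so these upper ends are not bounds.

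**Type I error.** With n1 portal patients and N COMBAT patients,

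r² = (1/n1 + DE/N) / (1/n1 + 1/N), and actual alpha = 2 × [1 − Φ(1.96 / r)],

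where N = 1,950 under A and 1,950 × DE under B. Example under A, n1 = 100, DE = 10.5: r² = 0.015385 / 0.010513 = 1.463, r = 1.210, 1.96 / 1.210 = 1.620, alpha = 10.5%.

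| Portal n | A, DE 1.3 | A, DE 3 | A, DE 5.5 | A, DE 10.5 | B, maximum |
|---|---|---|---|---|---|
| 50 | 5.1% | 5.6% | 6.3% | 7.8% | 5.3% |
| 100 | 5.2% | 6.1% | 7.6% | 10.5% | 5.5% |
| 200 | 5.3% | 7.2% | 10.0% | 15.3% | 6.1% |

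Under A the error reaches 6% at DE 4.4, 2.8 and 1.9 for 50, 100 and 200 portal patients. At ICC 0.50 that is about 8, 4.5 and 3 patients per provider.

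Other ICC readings: ICC 0.70 with m = 20 (DE 14.3) gives 9.0%, 12.7% and 19.0% under A. If the acceptance ICC refers only to patients who received an offer, the total-sample ICC is about 0.26-0.40 and DE about 1.3-8.6.

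**Simulation check** (beta-binomial COMBAT of about 1,950 patients, 15.4% in both groups, m = 2 and 20, ICC 0.30 and 0.50), type I error:

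| Portal n | Plain, independent patients | Plain, clustered | Effective-count, clustered | GEE robust Wald, clustered |
|---|---|---|---|---|
| 50 | 4.6% | 4.9-7.8% | 4.8-5.0% | 6.3-7.4% |
| 100 | 4.9% | 4.9-10.8% | 4.8-5.1% | 5.3-6.2% |
| 200 | 4.9% | 5.2-15.6% | 4.9-5.1% | 5.1-5.5% |

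At 2 patients per provider the effect is negligible. With 50 portal patients the error then stays just under 5%, because the discrete test starts at 4.6%.

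**At 29% versus 15.4%, if binomial intervals are used.** Variance of the difference = 0.29 × 0.71 / n1 + DE × 0.154 × 0.846 / N. With n1 = 100 under A:
- DE 1: 0.002059 + 0.000067, SE 4.61 points, lower limit 13.6 − 9.0 = 4.6 points.
- DE 10.5: 0.002059 + 0.000702, SE 5.25 points, lower limit 13.6 − 10.3 = 3.3 points.

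Across DE 1.3 to 10.5 the interval should be 0.5-14% wider, and its nominal 95% coverage is 94.9% down to 91.5%. Under B it should be 0.4-1.5% wider, with coverage of 94.9% to 94.7%. With 50 portal patients and DE 10.5 under A, the lower limit falls from 0.9 points to zero.

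COMBAT supplies only 1.6%, 3.1% and 6.1% of the naive variance at 50, 100 and 200 portal patients, which is why the effect is limited when the portal sample is small.

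**The case against.** The strongest reply is that materiality is not demonstrated. Every sizeable figure needs reading A together with many patients per provider, a high observed-scale ICC or a larger portal sample, and the document gives no reason to prefer A to B. At ICC 0.30 under A, the simulated error at 50, 100 and 200 portal patients is only 5.2%, 5.6% and 6.2% with 5 patients per provider, and 5.9%, 6.5% and 8.0% with 10. At 29% versus 15.4% with 100 portal patients, the plain and corrected tests then disagree in about 1.0% and 2.7% of studies. The SAP calls its own sample small, and no interval in it is shown to be wrong.

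All of that stands as a limit on size. It does not remove the fault. The SAP fixes a test whose independence assumption its own background contradicts, and the error can only go one way. Nor is this detail that a protocol would normally supply, because the primary test is what an SAP exists to fix.

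It can also be said that other cluster-aware methods would serve, and that the sandwich variance advised for the sensitivity model was not simulated in its weighted and imputed form. Both are fair. The effective-count test is preferred for the primary analysis because the GEE robust Wald test ran above 5% at 50 and 100 portal patients. For a weighted logistic sensitivity model, sandwich variance is standard, but its small-sample behaviour should be kept in mind.

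**Conclusion.** The concern holds. As written, the primary test understates COMBAT's variance, and nothing elsewhere in the SAP corrects it. The omission and its direction are certain for any positive ICC with more than one patient per provider. The size runs from negligible to material and depends on inputs the SAP does not state: negligible at 2 patients per provider, small if the quoted COMBAT interval is already cluster-adjusted, and a doubling or tripling of the nominal 5% in the upper scenarios with 100 or 200 portal patients.

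At the anticipated difference the conclusion would usually stand. With 100 portal patients under reading A, the plain and corrected tests disagree in about 0.3% of simulated studies at DE 1.3 and about 10% at DE 10.5. The omission matters most for a smaller observed difference, a larger portal sample or many patients per provider. It should be fixed before the data are analysed.

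**What to change.** Primary outcome: replace the plain chi-square with a Rao-Scott (effective-count) chi-square.
- Estimate COMBAT's design effect as the cluster-robust variance of its acceptance proportion divided by the binomial variance, with a floor of 1. Cluster by provider, or by the randomised unit if that lies above provider.
- Divide COMBAT's n and its number of acceptances by the design effect, and run the chi-square at 0.05 on those counts and the raw portal counts. Both estimated proportions are unchanged, and with a design effect of 1 this is the planned test.
- Compute the COMBAT interval (Wilson) and the difference interval (Newcombe) from the same effective counts.

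Sensitivity analysis: fit the propensity-weighted logistic regression with sandwich variance on the same clusters, each portal participant being their own cluster, within each imputed dataset, and pool by Rubin's rules.

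State COMBAT's n, the number of providers, the randomised unit, and whether 13.9% to 17.1% is cluster-adjusted.

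Cost: SAP wording and a few lines of code. Provider identifiers must exist, since provider-level ICCs were estimated. The difference interval becomes somewhat wider. In simulation at 29% versus 15.4% with 100 portal patients, power is 91.1% instead of 91.4% at DE 1.3, and 77% instead of 87% at DE 10.5.

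### Does the sensitivity analysis switch from acceptance to a different outcome by calling it adoption?

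*SAP*

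**What the plan says.** Four places in the SAP bear on this.

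- **Project background, opening:** "We will measure the adoption of the alcohol resource in the patient portal by examining analytics data". The data are collected passively by the portal.
- **Project background, next paragraph:** the aim is narrowed to a comparison with the earlier cluster randomised trial, COMBAT: "Specifically, we will test whether more eligible STOP patients accept the alcohol resource with the patient portal" than did so when providers made the offer.
- **Outcomes:** the primary outcome is acceptance of the offered intervention, meaning a 'yes' to "Are you interested in receiving some information about alcohol and smoking and about ways of reducing alcohol use". The only other listed outcome is continued participation in smoking cessation treatment.
- **Analysis plan:** the primary comparison is a chi-square test of two proportions, and "We will use a significance level of 0.05 and will derive confidence intervals around both proportions and around the difference between them". The sensitivity analysis begins "To examine the potential sensitivity of this result to case-mix differences" and continues "we will use logistic regression to compare adoption in this sample to that among COMBAT participants with AUDIT scores of 8 or higher", with propensity score weighting and multiple imputation.

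Adoption is not defined anywhere in the SAP, nor is it expressly equated with acceptance.

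**The concern.** A sensitivity analysis for case-mix should change the adjustment and hold the outcome fixed. Here the outcome has a different name, and the background links that name to analytics data rather than to a survey answer. Someone can say 'yes' to receiving information and never open it. If adoption meant use of the resource, a gap between the primary and the weighted results could come from the outcome, from the effect scale (an odds ratio against a difference in proportions) or from case-mix, and the reader could not tell which.

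The comparison is with a historical group and is not randomised, and this is the only case-mix adjustment the SAP describes for it, so an ambiguous dependent variable would matter. If instead adoption is just another word for acceptance, the stated intention to measure adoption rests on an expression of interest, and neither listed outcome records use.

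**Working it through.** **1. The SAP's own figures.** The inputs, all from Project background, are a COMBAT offer rate of 52.7% among those scoring 8 or more on the AUDIT-10, acceptance of 15.4% of the total sample, and acceptance of 29% among those offered.

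- 15.4 / 52.7 = 29.2%, which agrees with the stated 29%.
- In reverse, 0.527 × 0.29 = 15.3%, which agrees with 15.4% within rounding.

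The 15.4% therefore shares its denominator with the 52.7%, namely COMBAT participants scoring 8 or more. That is the group named as comparator in the sensitivity analysis, and the uptake figure the SAP gives for it is an acceptance figure.

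**2. The two readings side by side.**

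| Text | Adoption = acceptance | Adoption = recorded use |
|---|---|---|
| Check is aimed at the primary result | fits | does not fit |
| Background narrows adoption to a test of accepting | fits | does not fit |
| Compared with COMBAT, where providers made the offer | COMBAT figure given (15.4%) | no COMBAT figure given |
| Adoption measured from portal analytics | possible, if the portal logs the 'yes' | fits |

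Only the last row favours the second reading, and it does not exclude the first. The SAP does not say how the 'yes' is recorded, and nothing in it rules out the portal data.

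**3. Would the definition change the conclusion?** Let u be the share of those saying 'yes' who go on to use the resource. The SAP gives no value, so 0.5 to 0.8 is an assumption. Assume also that only those who say 'yes' use it.

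- This study: 0.29 × 0.5 = 14.5% and 0.29 × 0.8 = 23.2%.
- Break-even with COMBAT's 15.4%: 0.154 / 0.29 = 0.53.

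This seems to show that the result can reverse, but it sets use in one study against acceptance in the other. With the same u in both:

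- COMBAT: 0.154 × 0.5 = 7.7% and 0.154 × 0.8 = 12.3%.
- Ratio of use: 29 / 15.4 = 1.88, whatever u is.
- Difference: 14.5 − 7.7 = 6.8 points and 23.2 − 12.3 = 10.9 points, against 29 − 15.4 = 13.6 points for acceptance.

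The difference shrinks but keeps its direction. A reversal needs a lower u here than in COMBAT, or a change of definition between cohorts. The SAP plans no such change.

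**4. Effect scale.** At the SAP's figures the difference is 13.6 points and the odds ratio is (0.29 / 0.71) / (0.154 / 0.846) = 2.24. These are two summaries of the same pair of proportions. A weighted logistic model whose only term is study has fitted probabilities equal to the weighted proportions, so the weighted difference comes from the same fit.

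**The case for a change.** The strongest case for a change is that the SAP should fix one dependent variable before data are seen and, on its wording, leaves two candidates. The mismatch lies within the SAP, so the protocol need not be seen to notice it. The correction would take a few words, and the analytics are being collected anyway.

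What stands is that the term is used loosely and is undefined. The two candidates are not equally open, however. For use of the resource, the SAP offers no COMBAT counterpart, so the planned comparison could not be made from what it describes.

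On scale, the SAP does not restrict the logistic analysis to an odds ratio, so asking for a weighted difference is a preference about reporting.

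On the absence of a use outcome, the SAP chooses acceptance as its primary outcome and declines to evaluate efficacy. A use outcome would be an additional endpoint with no COMBAT comparator in the SAP, and outcome lists are commonly left to the protocol.

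The argument that a 'yes' rate can only overstate uptake assumes that the resource is reachable only after a 'yes', which the SAP does not state.

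**Conclusion.** The concern is right that the SAP uses two words for what appears to be one outcome. It does not show that the sensitivity analysis tests a different endpoint or fails to check the primary result. An analyst following the plan would take the 'yes' response as the dependent variable in both cohorts, because it is the outcome of the result being checked and the only one with a COMBAT figure in the SAP. On that reading, writing acceptance for adoption would be tidier but would alter no estimate, interval or conclusion, so the numerical effect is nil.

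This rests on two assumptions: that adoption is a synonym for acceptance, which the text favours without stating it, and that conclusions will be worded as acceptance rather than as use. If the protocol defines adoption separately as recorded use, with a COMBAT counterpart, the point would need another look. Nothing in the SAP suggests that it does.

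### The secondary comparison defines its two groups by different rules, so any step needed to become a participant would filter only the post-launch group

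*SAP*

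**What the plan says.** The Outcomes section names the secondary outcome as "continued participation in smoking cessation treatment". Under Secondary outcome in the Analysis plan it becomes non-attendance at a clinical visit, and the stated aim is to "compare the proportion of participants who do not attend a clinical visit after self-enrolling to that among people self-enrolling before the study began". The earlier group is limited to those "who would have met study criteria". After launch, then, a person counts by being a participant; before launch, by having self-enrolled and been eligible.

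Only the first visit is considered: "We will not examine longer-term retention due to the study timeline and the expectation that effects would be visible at the first contact".

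The Project background says that the study "will make the offer to all participants". The SAP does not say whether every eligible self-enrollee after launch counts as a participant.

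The only case-mix adjustment is under Sensitivity analysis, where "we will use propensity score weighting to adjust for age, gender, heaviness of smoking, AUDIT scores, education, income, and comorbid conditions". That adjustment belongs to the acceptance comparison with COMBAT. None is stated for the secondary outcome.

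**The concern.** The earlier group could not have joined the study, so no participation step can have acted on it. It contains every self-enrollee who meets the criteria, including those who would not have consented or finished the portal items. If such a step exists after launch, its counterpart group has been through a filter that the earlier group has not.

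The filter would act on engagement, which is close to what first-visit attendance measures. An eligible self-enrollee who does not become a participant and never attends is left out after launch, while the same kind of person is counted as a non-attender before launch. Participants would then probably show less non-attendance than the earlier group even if the offer did nothing.

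This outcome is the one in the SAP that bears on whether adding an alcohol offer to the portal affects engagement with smoking treatment. An error in the reassuring direction would undermine it.

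**Working it through.** The SAP gives no non-attendance rate, participation rate or sample size for this outcome, so there is no stated figure to reproduce. The check is algebraic, and all numerical inputs are assumptions.

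**Definitions**

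- f: share of eligible post-launch self-enrollees who do not become participants.
- p: non-attendance that participants would have without the offer.
- m: non-attendance among eligible non-participants.
- d = m − p: the gap between them.
- q0: non-attendance among all eligible self-enrollees before launch.

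**No effect of the offer.** If the two periods are otherwise alike, the earlier group is the mixture q0 = (1 − f)p + f·m. The planned comparison then shows

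p − q0 = −f(m − p) = −f·d.

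Spurious fall in non-attendance, in percentage points, over assumed ranges:

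| f | d = 10 | d = 20 | d = 30 |
|---|---|---|---|
| 10% | 1 | 2 | 3 |
| 20% | 2 | 4 | 6 |
| 30% | 3 | 6 | 9 |
| 40% | 4 | 8 | 12 |

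**Cross-check from the mixture.** Take q0 = 30%, f = 20% and m = 70%. Then p = (0.30 − 0.20 × 0.70)/0.80 = 0.20, so the comparison shows 20% against 30%, a false 10-point improvement. The product formula agrees: 0.20 × (70 − 20) = 10 points. This gap of 50 points is larger than any in the table, and the example serves only to confirm the formula.

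**A real effect of the offer.** Suppose the offer raises non-attendance among participants by e points.

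- Planned comparison: e − f·d. With f = 20% and d = 20, a true rise of 4 points gives 4 − 4 = 0.
- All eligible self-enrollees in both periods: (1 − f)e. The same case gives 0.80 × 4 = 3.2 points, diluted but with the right sign.

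**When there is no bias.** The term f·d is zero if f = 0 (every eligible self-enrollee is a participant) or if d = 0 (non-participants attend as often as participants). If d were negative, the bias would reverse.

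**Would the planned weighting help?** It is not planned for this comparison. If it were extended to it, it could account only for differences carried by the measured covariates. It would not bring back eligible people who were never counted.

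**The case against.** The strongest reply is that the SAP describes no participation step at all. It mentions no consent, opt-in or completion requirement. It says that portal analytics are gathered passively, and it frames the primary question in terms of eligible STOP patients. On that reading participants are simply the eligible self-enrollees, f is zero and the comparison is like for like. Enrolment procedures also normally belong in the protocol. This stands as a limit: the bias is conditional. It does not remove the point, because the analysis denominator is set in the SAP, the two groups are worded differently in one sentence, and nothing equates them. The remark about passive collection concerns adoption of the alcohol resource, not who is counted here.

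A second reply is that applying study criteria to the earlier group already aims at symmetry. If those criteria include completing portal items that existed before launch, the same filter acts on both sides. That is possible, but the SAP does not list the criteria, and a consent step could not be mirrored in any case.

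A reader might also infer something stronger: that people put off by the alcohol question drop out of the count, so a deterrent effect is hidden. The text does not support this. If the study "will make the offer to all participants", a person reaching the offer is already a participant, so those who decline or leave there should remain in the denominator with their non-attendance counted. Those lost would have been lost before the offer and cannot have been deterred by it.

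**Conclusion.** The point holds in conditional form. The two groups are defined by different rules, and any step between eligible self-enrolment and participation would filter the post-launch group alone. The likely result is a spurious fall in non-attendance of f·d: 4 points at f = 20% and d = 20, and 1 to 12 points over f of 10–40% and d of 10–30 points. These ranges are assumed, so the figures show how the bias scales and are not an estimate for this study.

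The direction rests on the assumption that non-participants attend less often, which is plausible but not shown in the SAP. A bias of this kind could offset a true adverse effect on attendance; the SAP does not support saying that it will. People who abandon self-enrolment itself are missing from both groups and play no part in this point.

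**What to change.** Define both groups by one rule: all people who self-enrol in the period and meet the study criteria, using only criteria that can be assessed in both periods. Count first-visit non-attendance from self-enrolment, with the same visit window in each period. Report the participants-only figure as supportive. If every eligible self-enrollee is in fact a participant, the SAP should say so; the two definitions then coincide.

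The work is a change of wording plus one aggregate count of eligible self-enrollees and first-visit attenders in the study period. The plan already relies on information about people outside the study for the earlier group, so the same kind of source should serve.

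There are two costs. Any real effect is diluted in proportion to the share who never received the offer: at f = 20% the comparison retains 80% of it, at f = 40% only 60%, so the dilution is not always slight. Use of aggregate data on non-participants may also need confirmation from the ethics board.
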